**\*\*\*\* General practitioner of Brawijaya University Hospital, Malang, East Java, Indonesia**

**Brawijaya University Hospital**

**18 August 2024**

## **Background**

This study was conducted at Brawijaya University Hospital in Malang, Indonesia, involving 35 patients with parkinsonism. The study used a prospective cohort study design. The effects of oxyhydrogen nanobubble (OHNB) infusion on the subjects were observed without comparison to a control group (placebo). Pre- and post-test results were evaluated before and after the OHNB infusion.

The variables analyzed in this study were the degree of parkinsonism using the Hoehn and Yahr scale, cognitive function using the MOCA-Ilna test, and quality of life for patients with parkinsonism using the PDQ-39 questionnaire.

The hypothesis of this study is that OHNB infusion can improve disease severity, cognitive function, and quality of life in patients with parkinsonism..

OHNB is an infusion that containing H2 and O2 gas molecules in the form of nanobubbles. H2 and O2 gas molecules encapsulated in nanobubbles are more stable and can persist for longer periods in solution (Li et al., 2022) and more easily penetrate the blood-brain barrier (Owen et al., 2016; Alghamdi et al., 2022). H2 nanobubbles have superior antioxidant properties than H2 water alone (Kato et al., 2015). H2 have anti-inflammatory effects, thus reducing cellular inflammation (Cheng et al., 2023), reducing oxidative stress and protecting the brain from ischemic injury (Ohsawa et al., 2007), mitigating acute neurotoxic effects, and addressing behavioral disorders caused by MPTP exposure on dopaminergic neurons (Fujita et al., 2009). O2 is required to activate the HIF-1 $\alpha$  pathway which can maintain neuronal integrity.(Pinilla et al, 2021)

## **Study Purpose**

The aim of this study was to determine the effect of oxyhydrogen nanobubble infusion on the degree of disease, cognitive function, and quality of life of patients with parkinsonism.

## **Study Design**

The study used a prospective cohort study design. The effects of oxyhydrogen nanobubble (OHNB) infusion on the subjects were observed without comparison to a control group (placebo). Pre- and post-test results were evaluated before and after the OHNB infusion.

### **Inclusion Criteria**

- Patients who meet the criteria for parkinsonism
- 18-70 years old

### **Exclusion Criteria**

- Patient is unwilling to undergo examination.
- Pregnancy.
- History of malignancy and/or chemotherapy.
- History of alcohol or drug use that can induce extrapyramidal symptoms.
- Hyperthyroidism.
- Impaired kidney function.
- Impaired liver function.
- Patients with heart failure requiring fluid restriction.
- MRI results suggest a brain tumor causing parkinsonism symptoms.
- Catalase enzyme deficiency (acatalasemia).

### **Data Analysis**

Data regarding age, gender, duration of parkinsonism symptoms, types of medications consumed, comorbidities (hypertension, coronary heart disease, metabolic syndrome), degree of parkinsonism according to the Hoehn and Yahr classification, cognitive function according to the MoCA-Ina examination, and PDQ 38 examination results in this study will be presented in a frequency distribution table. Then, the table will be analyzed descriptively.

Data regarding parkinsonism severity examination based on Hoehn and Yahr scale, MoCA-Ina examination, and PDQ 39 questionnaire examination PDQ-39 pre and post treatment are numerical data consisting of three groups of data, namely pre-treatment data, evaluation data after the 7th injection (mid-treatment data), and evaluation data after the 12th injection (post-treatment data). will be analyzed statistically using one-way ANOVA. The data will then be analyzed whether they are normally distributed or not. If the data are normally distributed, they will be analyzed using Repeated ANOVA Test, and if they are not normally distributed, they will be analyzed using Friedman Test.

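### The planned overall tests across three visits do not test improvement from before treatment to after the 12th infusion, and no rule says which of three equal outcomes must be positive

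*Combined protocol and SAP*

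**What the plan says.** The Background section states a directional aim: "The hypothesis of this study is that OHNB infusion can improve disease severity, cognitive function, and quality of life in patients with parkinsonism". The Expected Results section repeats it. Three outcomes are listed side by side (Hoehn and Yahr, MoCA-Ina and PDQ-39), and none is called primary.

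The Data Analysis section describes three sets of measurements per patient: "namely pre-treatment data, evaluation data after the 7th injection (mid-treatment data), and evaluation data after the 12th injection (post-treatment data"). It first says that these "will be analyzed statistically using one-way ANOVA". After a normality check it says of normally distributed data that "they will be analyzed using Repeated ANOVA Test, and if they are not normally distributed, they will be analyzed using Friedman Test". Each of these is an overall comparison of three visits.

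The document gives no contrast between the first and last visit, no follow-up test, no effect estimate or confidence interval, no significance level, no multiplicity adjustment, and no rule for how many outcomes must be positive. The Background section gives the size, "involving 35 patients with parkinsonism", and the Study Design section says that the effects are "observed without comparison to a control group (placebo").

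**The concern.** The claim to be made is that patients are better after the course than before it. The null hypothesis of repeated-measures ANOVA and of the Friedman test is that all three visits are alike. It can be rejected because patients worsened, or because they changed at mid-treatment and returned to where they began. An analyst who follows the plan exactly would finish without having tested the claim.

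This matters more than usual here. In a single-group study the size and direction of the pre-to-post change is the central evidence, and the plan does not say how that change will be estimated.

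The second part is the claim rule. With three outcomes of equal standing, a reader cannot tell whether one significant result is enough or all three are needed. The chance of error differs greatly between the two.

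**Working it through.** The plan gives no significance level, power or effect size, so it has no figure of its own to reproduce.

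**Inputs from the document:** n = 35; three visits; three outcomes; no control group.

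**Assumptions:** 0.05 per test; complete, normally distributed data; equal variance and equal correlation ρ between visits, with ρ from 0.5 to 0.9; changes in units of the SD between patients at one visit; correlation between outcomes from 0 to 0.9.

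**1. What a significant overall test can mean**

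For repeated-measures ANOVA the noncentrality is λ = n × Σ(μ_j − μ̄)² / (1 − ρ), with 2 and 2 × 34 = 68 degrees of freedom and a critical F of 3.13.

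- Mid-treatment change only, visit means (0, 0.3, 0): deviations −0.1, 0.2, −0.1; sum of squares 0.06; λ = 35 × 0.06 / (1 − ρ) = 2.1 / (1 − ρ).
- Worsening at the final visit only, (0, 0, −0.3): deviations 0.1, 0.1, −0.2; sum of squares again 0.06, so λ is the same.

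| ρ | λ | Chance that the overall test is significant (either pattern) |
|---|---|---|
| 0.5 | 4.2 | 41.7% |
| 0.6 | 5.25 | 50.6% |
| 0.7 | 7.0 | 63.5% |
| 0.8 | 10.5 | 81.7% |
| 0.9 | 21.0 | 98.6% |

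In the first pattern the true pre-to-post change is zero, so a paired test of that change would reject in only 5% of trials.

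The Friedman branch behaves alike. In 20,000 simulated trials with a shift of 0.5 within-patient SD at the mid visit only, ANOVA was significant in 55% and Friedman in 42%. A worsening of that size at the last visit gave 55% and 42%.

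**2. Power of the overall test against a post-minus-pre contrast**

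The paired t contrast has noncentrality 0.3 × √35 / √(2(1 − ρ)), which is 2.81 at ρ = 0.8. The critical t is 2.03 on 34 degrees of freedom.

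| Pattern, ρ = 0.8 | Overall test | Contrast |
|---|---|---|
| Linear (0, 0.15, 0.3), λ = 35 × 0.045 / 0.2 = 7.875 | 69% | 78% |
| Step at mid, held (0, 0.3, 0.3), λ = 10.5 | 82% | 78% |
| Step at end (0, 0, 0.3), λ = 10.5 | 82% | 78% |

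Neither test is better in general.

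**3. Three outcomes**

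If the outcomes are independent, 1 − 0.95³ = 14.3%. Under no change, 20,000 simulated trials per setting (Monte Carlo error about ±0.5 points) gave:

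| Outcome correlation | Any significant, ANOVA | Any significant, Friedman | Any significant with post better than pre, ANOVA | All three significant, ANOVA |
|---|---|---|---|---|
| 0 | 14.0% | 14.0% | 7.1% | 0.0% |
| 0.3 | 14.1% | 13.7% | 7.1% | 0.04% |
| 0.5 | 13.0% | 13.5% | 6.7% | 0.3% |
| 0.6 | 12.1% | 12.9% | 6.0% | 0.4% |
| 0.7 | 11.0% | 12.2% | 5.6% | 0.8% |
| 0.8 | 10.2% | 11.4% | 5.1% | 1.4% |
| 0.9 | 8.6% | 10.4% | 4.4% | 2.0% |

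These rates apply to the repeated-measures tests. One-way ANOVA, which the section names first, ignores the pairing. Applied literally, it gave about 0.05% for any false result at an assumed within-patient correlation of 0.7. Ties on the coarse Hoehn and Yahr scale could shift the actual rates.

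**The case against.** The strongest reply is that an overall test followed by a look at the visit means is ordinary practice. The plan also promises descriptive tables, so direction could be read from the summaries, and pairwise follow-up could be added. That is fair, and it rules out saying that the study cannot show improvement. What stands is that no such step is written down, so the comparison that decides the claim would be chosen after the results are known.

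Four stronger readings that a reader might infer are not supported:

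- *The chance of falsely claiming improvement is 12-14%.* That range counts significant results in either direction, and it rests on a level of 0.05 that the document never states. Results pointing to improvement are about half of it.
- *Any one outcome is enough for the claim.* The hypothesis joins the three with the word and: "OHNB infusion can improve disease severity, cognitive function, and quality of life in patients with parkinsonism". If all three must be significant, the error is at most about 2%. The defect is that no rule is given.
- *The overall test has less power for the question of interest.* It does for a linear change, but it is slightly ahead for step changes, and the document gives no expected course over time.
- *The overall test detects harm more readily than benefit.* It does not. A given pattern and its mirror image have the same chance of significance.

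No within-patient correlation is given either, so no single figure from the first table should be quoted without the range.

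**Conclusion.** The point holds as a mismatch between claim and analysis. A significant result from the tests as written would not by itself support improvement after the 12th infusion, because it carries neither direction nor location. This follows from the nature of the tests and needs no assumed number.

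The size does rest on assumptions. Under a pattern with no pre-to-post change, the overall test is significant in about 42% to 99% of trials for within-patient correlations of 0.5 to 0.9 and a 0.3 SD mid-treatment change. At 0.05 per test with any one outcome sufficing, at least one false significant result occurs in about 12-14% of trials for outcome correlation up to about 0.6, and in about 9-11% (ANOVA) at 0.7-0.9. Of these, about half would point to improvement: 6-7% of trials up to a correlation of 0.6.

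Confidence is high for the missing contrast and claim rule, and moderate for the percentages. The plan should be changed; no new data are needed.

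**What to change.** In the Data Analysis section:

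1. For each outcome, make the change from pre-treatment to after the 12th infusion the decision contrast and report it with a 95% CI. Use a paired t-test, or a Wilcoxon signed-rank test with a Hodges-Lehmann interval where the data are non-normal or ordinal, as with Hoehn and Yahr.
2. State which direction is beneficial on each scale, and claim improvement only if the change lies in that direction.
3. State the significance level. Either name one primary outcome before the data are seen, or apply Holm across the three contrasts (0.0167, 0.025, 0.05 in order of p-value).
4. Report changes to and from mid-treatment descriptively. The Study Protocol section places that visit after the sixth infusion and the Data Analysis section after the seventh; the two must be reconciled.

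**Cost.** A few sentences of text. The Study Protocol section already schedules all three instruments at both ends of treatment, so no patients, visits or measurements are added. Holm costs power: at its first step (0.05 / 3 = 0.0167, critical t 2.52), power for a 0.3 SD change at correlation 0.8 falls from 77.8% to 61.5%. Naming one primary outcome avoids that loss.

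**What it does not do.** Without a control group the contrast shows change from baseline. It does not attribute that change to the infusion, and the conclusions should say so.

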## Expected Results

Oxyhydrogen nanobubble infusion can improve disease severity, cognitive function, and quality of life in patients with parkinsonism.

## Ethical Considerations

This research upholds research ethics so that it can provide values that benefit the wider community. The results of this study are expected to have a positive impact on the Indonesian health system, making it more independent and accessible to the people. However, a potential risk posed by this study is the possibility of a healing crisis, in which participants experience a decline in physical condition such as fever, chills, and pain. After experiencing a healing crisis, participants can experience the benefits of oxyhydrogen nanobubble infusion, such as feeling much healthier, more energetic, and refreshed than before the infusion. This risk can be managed with the guidance and prescription of medication provided by a doctor, thereby minimizing the occurrence and severity of a healing crisis.

